Protocol Elements Checklist for:

Single-dose Intraoperative Methadone for Early Ambulation and Sustained Pain Control in Spinal Fusion Surgery Patients

1) Background/Significance

Methadone is a synthetic opioid analgesic with agonist properties at the μ -opioid receptor binding site that has long been used as an alternative to morphine and hydromorphone in patients with severe pain. It has a diffuse bioavailability and is highly efficacious through its oral form, yet its bioavailability is heavily dependent on variability in cytochrome P450 3A4 activity, and is quite variable amongst individuals. Methadone reaches peak plasma concentrations in 2.5 to 4 hours after oral administration, has a rapid onset, has a half-life is between 20-35 hours (range 5-130 hours), and analgesia may be reported for up to 108 hours after a single dose. Repeated dosing during this interval may result in drug accumulation and an increased risk of adverse reactions.

Methadone has an asymmetric carbon skeleton with two carbon side chains which allow for two enantiomeric forms, the D- and L-isomers, and while the racemic mixture is administered, only the L-isoform seems to have clinical activity. The binding of the D-isomer, while not implicated in pain control may influence opioid potentiation and tolerance by binding to the NMDA receptor. Methadone's NMDA receptor site antagonism acts to inhibit enzymes such as adenyl cyclase and their downstream production of secondary signaling molecules like cyclic AMP. This activity may attenuate opioid tolerance and opioid abstinence syndrome as NMDA receptor agonism has been implicated in the development of hyperalgesia, acute and chronic tolerance, and chronic pain states. Its antagonisms may explain the low rate of dependence seen with methadone.

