• Describe predictors of interest along with potential confounders and effect modifiers Predictors of interest include drug abuse history and/or behavior, as well as anticipated benefit from history of medication usage in the literature. Potential confounders include previous narcotic use history, narcotic tolerance/dependence in patients not otherwise excluded during recruitment, variable pain thresholds and tolerance amongst different patients, duration and complexity of surgeries, as well as variable renal clearance. Many of these are also effect modifiers.

• Describe matching criteria, if applicable

Matching criteria will not be used at this study will be structured as a randomized control trial.

• Describe duration of follow-up, and timing of data collection

Post-operative imaging will be reviewed to determine successful decompression and instrumentation. Data collection will be done during patient's hospital stay. Patients will be asked about their post-operative pain at 4 hour intervals, and data regarding their overall narcotic usage and their time to ambulation will be recorded from the medical record. Follow-up will then consist of: 1 week for phone call by spine NP, 2 week evaluation as is standard for all post-operative patients.

• Describe the planned interventions and their timing.

A study participant will be randomized ahead of time to be administered methadone or the current standard of care in blocks of 5 blinded to clinical personnel. If the patient is assigned to the methadone group, the anesthesiology team will be given this information and the anesthesiologist assigned to the Revised 4/17/13, 6/23/15

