The sample size was determined using the Gottschalk study listed in the reference section which used methadone vs. sufentanil in 29 patients undergoing lumbar fusion surgery and the measures for pain level and total narcotic usage at 48 hours to determine an 'n' for the total study population, using a power of 0.80. The details of the calculations is listed in the data analysis section (7a) below and calculated with the suggestion of the statistician on the IRB. The assumptions with which the outcomes are hypothesized are the result of previously published data using similar populations. Two sample t-tests are appropriate to determine statistical significance between mean pain scores between different patients in the control and study groups for each individual time point as there will be no censoring of the study data. Ranked T-test may also be used if outliers are present, however patients with unusual post-operative courses may be excluded if their reason for prolonged hospitalization is unrelated to immediate post-operative pain

control. The large sample size plans to take into account possible outliers that may not be included in final analysis, despite their mention in study write-up to determine why their post-operative hospitalization was prolonged. Additionally, data about patients' mean time to ambulation, mean time to discharge, and mean overall narcotic usage will be measured between the control and study populations. Data analysis will be performed with the assistance of the biostatistician listed as a member of the study team, [name], from the Albert Einstein College of Medicine, Division of Biostatistics. Thus, a sample of 60 completed methadone patients will be evaluated against 60 randomized, standard narcotic regimen controls. The mean data for control patients' pain ratings, narcotic usage, time to ambulation, and time to discharge will be obtained, the statistical deviation of this data will be measured and compared to subject data in all facets.

• Take into account anticipated drop-out or loss-to-follow up rate.

We intend to screen 200 patients to have 60 in each arm ultimately included in the study. Since the intervention is a single intra-operative occurrence, that when completed patients cannot reverse, we do not anticipate any drop-out. A two week follow-up visit is a required standard of care for all post-operative patients, without patient loss to follow-up historically. The study is completed at this point.

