interim analysis is negligible. If the methadone intervention contributes greater than normal adverse events (>2 patients) the study will be held from further recruitment. The study medication will not be administered further, no dosing changes will be made, and the IRB will be informed. A decision at this point will be reached regarding further accrual. If a patient should die prior to discharge, a thorough cause analysis will be implemented by the DSMB, the IRB, in addition to the analysis that will already be performed by the hospital. If it is due to the surgery outside of the trial mediation, the data for this patient will not be used and the information will be explicitly reported in any publication yet kept separated from the other patient's data, as it would not be feasible or make sense to include this patient in the analysis. If this adverse event is found to be caused by the methadone administration, the trial will be stopped. This is however an extremely unlikely scenario as methadone is used daily by millions of individuals, has already been approved by the FDA, and our study patients will undergo a rigorous screening, namely for QTc prolongation, to remove any potential risk of death as a result of methadone administration. The only wayy to address this possibility is to have a plan to remove this patient's data from the other patient's data, with a clear note made in the report.

Describe how possible confounding and/or effect modification will be addressed. The possible confounders have been addressed via the strict inclusion and exclusion criteria of the study. Other confounding variables including past narcotic usage, and a cutoff of <10mg equivalents of morphine will be considered when selecting patients for participation in this study. Such a low daily morphine dose is unlikely to significantly impact methadone effect or post-operative narcotic use in patients with this low level of narcotic usage compared to narcotic-naïve patients. Patient time to ambulation will be confounded by baseline neurological status and therefore we will randomly assigning patients to each arm of the study as described above. Confounding in regards to time of operative procedure and complexity of surgery will be controlled properly with appropriate randomization.

Describe how loss to follow up will be addressed

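### The death review and its stopping rule end at hospital discharge, and no common safety window after discharge is defined, although length of stay is itself an outcome

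*Combined protocol and SAP*

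**What the plan says.** **Deaths.** Section 7, under interim analyses or early stopping: "If a patient should die prior to discharge, a thorough cause analysis will be implemented by the DSMB, the IRB". Two consequences follow in the same paragraph. If surgery rather than the trial drug was the cause, the patient's data are set aside and reported separately. If methadone was the cause: "If this adverse event is found to be caused by the methadone administration, the trial will be stopped".

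**Other adverse events.** The same paragraph has a second rule: "If the methadone intervention contributes greater than normal adverse events (>2 patients) the study will be held from further recruitment". It states no time limit.

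**When data are collected.** Section 2, on duration of follow-up: "Data collection will be done during patient's hospital stay". The paragraph goes on: "Follow-up will then consist of: 1 week for phone call by spine NP, 2 week evaluation as is standard for all post-operative patients". Section 2, on the planned interventions, says that adverse events will be recorded and gives no end date; it also mentions routine clinic returns at 2 weeks and 3 months. Section 3, on drop-out, says of the 2-week visit: "The study is completed at this point".

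**The drug.** Section 1 gives a "half-life is between 20-35 hours (range 5-130 hours), and analgesia may be reported for up to 108 hours after a single dose". A spinal fusion series described in the same section had a mean half-life of 21±13 h, range 5-48 h.

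**Length of stay.** Section 7 hypothesises fewer hospital days on methadone. It gives a standard deviation of 6.7 days for time to discharge and a detectable reduction of 3.8 days, but no mean or median stay.

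**The concern.** Two things are at stake.

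The first is the death rule. Its reach is set by where the patient is, not by time since the drug was given. Someone who goes home early and dies within the following days is still in the study, but the plan requires no cause analysis by the monitoring committee and no decision on stopping.

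The second is the comparison of safety between arms. Discharge is an outcome that methadone is hypothesised to bring forward. If harm is counted only until discharge, treatment can shorten the time during which harm is looked for, and it would do so in the arm given the long-acting drug. A lower event count on methadone could then partly reflect less observation.

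**Working it through.** **1. Reach of each rule.**

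| Event | Death review and stop | Adverse-event hold (>2 patients) |
|---|---|---|
| One death before discharge | applies | one patient, not reached alone |
| One death from discharge to the 2-week visit | does not apply | one patient, not reached alone |
| Non-fatal over-sedation, before or after discharge | not a death | counts towards the total in either case |

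The uncovered case is the second row. The hold needs at least three patients, so one late death does not trigger it.

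**2. Do the data-collection statements agree?** One sentence in section 2 puts data collection in the hospital stay. The next sets a 1-week call and a 2-week evaluation. The interventions text records adverse events without an end date. Section 3 closes the study at 2 weeks, while the secondary outcomes include fusion at 3-6 months. Nowhere is the safety content of the call or visit given, or an adverse-event window common to both arms. The text can be read as in-hospital only or as 2 weeks.

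**3. Could drug effect outlast an early discharge?** Inputs are the section 1 half-lives. Fraction remaining = 0.5^(t / half-life), a simple first-order approximation that ignores distribution. For example, at 72 h with 35 h: 0.5^(72/35) = 0.24.

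| Half-life | Source in section 1 | 48 h | 72 h | 108 h |
|---|---|---|---|---|
| 5 h | lower end of both ranges | 0.1% | 0.0% | 0.0% |
| 20 h | main range, low | 19% | 8% | 2% |
| 21 h | spinal fusion series, mean | 20% | 9% | 3% |
| 35 h | main range, high | 39% | 24% | 12% |
| 48 h | spinal fusion series, maximum | 50% | 35% | 21% |
| 130 h | upper end of wide range | 77% | 68% | 56% |

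The longest reported analgesia, 108 h, is 108/24 = 4.5 days.

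**4. The plan's discharge figures.** Detectable reduction = effect size × SD: 0.56 × 6.7 = 3.75, stated as 3.8 days; 0.74 × 6.7 = 4.96, stated as 5.0 days. Both reproduce.

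**5. How unequal could a discharge-limited window be?** Two assumptions are needed, neither supplied by the plan: a control mean stay L, and a true reduction equal to the detectable 3.8 days. The methadone mean is then L − 3.8. Setting the mean stay against 4.5 days:

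| Assumed L (days) | Methadone mean (days) | Mean stay as share of 4.5 days: control | Methadone |
|---|---|---|---|
| 5 | 1.2 | 100% | 27% |
| 6 | 2.2 | 100% | 49% |
| 7 | 3.2 | 100% | 71% |
| 8 | 4.2 | 100% | 93% |
| 10 | 6.2 | 100% | 100% |

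Shares are capped at 100%. The methadone mean falls below 4.5 days when L < 3.8 + 4.5 = 8.3 days. This compares means only. With an SD of 6.7 days, a reduction in the mean could come largely from long stays and leave the first 4.5 days about equally observed.

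**The case against.** The strongest reply is that the plan does look beyond discharge, and much of that stands.

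- **A reader might infer that all data collection stops at discharge.** The documents do not support this. The sentence that suggests it is followed at once by the 1-week call and 2-week evaluation, and adverse-event recording has no end date. The statements are unreconciled; they do not add up to a stop at discharge.
- **A reader might infer that a readmission for over-sedation triggers nothing.** It can count towards the hold, which has no discharge limit. A single non-fatal event triggers nothing before discharge either, so the discharge wording is not the cause.
- **A reader might infer that methadone outlasts a typical discharge.** No typical stay is given. The largest residual fractions come only from the 130 h extreme; at 5 h almost nothing remains at 48 h. A residual fraction is also not a measure of harm, and the protocol ties the long half-life to lethargy and altered mental status, listing respiratory depression separately as a result of overdose.
- **A reader might infer that the safety comparison is biased towards methadone, by 3.8 days of observation.** That figure is a detectable difference, not an expected effect. The call and visit fall at the same times in both arms and could capture late events.

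What the reply does not answer is the death rule, which is explicitly limited to the stay and has no counterpart for the rest of the study. Nor does it supply the missing safety content of the later contacts.

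**Conclusion.** The point holds in limited form. The firm part rests on the text alone: one methadone-caused death after discharge but before the 2-week visit would trigger neither the cause analysis nor the stop, and would not by itself reach the hold. The half-life figures make this more than a formality, since 8% to 24% of a dose remains at 72 h over the main range, under simple decay.

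The conditional part is that safety events could be under-counted on methadone. It requires that events be counted only during the stay and that the hypothesised earlier discharge be real. Its size cannot be fixed from the documents: over assumed control mean stays of 5 to 10 days, the illustrative methadone share runs from 27% to 100%.

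No sample size or error rate is affected. Label: cheap improvement, should-fix.

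**What to change.** 1. **Death rule (section 7).** Apply the cause analysis and the methadone-death stop to any death from dosing to the 2-week visit. Do not simply substitute the new period throughout the paragraph: that would also widen the clause removing a surgical death's data, and would discard patients whose in-hospital outcomes are complete. State that the removal clause is not extended to them.
2. **One safety window (sections 2 and 3).** Reconcile the data-collection sentence, the open-ended adverse-event recording and the 2-week end of study into one fixed window, incision to the 2-week visit, whatever the discharge day. Methadone is given on incision, so this starting point serves both arms.
3. **Content.** Use identical scripted questions in both arms at the existing 1-week call and 2-week visit: excess sedation, breathing problems, naloxone use, emergency visit, readmission. Report the results by arm over the full window.

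The cost is protocol wording, a short script and slightly more data entry. A few more events unrelated to the study drug will be recorded. No visits are added, and the sample size is unchanged.

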Since the standard of care is narcotic usage to manage the significant pain that complex spinal surgery causes, it is understandable that methadone could be a desirable therapy to promote sustained pain control and early ambulation in these patients. It is our hypothesis that methadone use intraoperatively will result in earlier time to ambulate post op and better ability to participate with post-operative PT evaluation, lower narcotic usage, earlier discharge, and improved scores on clinical outcome scales including the Oswestry Low Back Pain Disability Questionnaire and the Short Form 36 Health Survery. It is also foreseeable that since methadone would be administered while the patient was sedated intraoperatively, it could prevent the association between the analgesia and euphoria that may result from self- or nurse-administered narcotics, such as with a PCA, which could promote early tolerance or reliance. Randomization of patients between methadone administration and standard intra-operative narcotic administration allows for controlled and accurate investigation of subjects compared to the current standard of care.

• Clearly state target population and recruitment methods

We would screen the first 200 consecutive patients to determine whether inclusion criteria are met, with an end goal of 120 patients who will complete the study and 60 control subjects who receive the current standard of care in a 1:1 randomized fashion. Patient will be recruited in office at time of consent for surgery by the principal investigator.

• State inclusion/exclusion criteria clearly

Inclusion criteria:

Patients undergoing elective lumbar transforaminal interbody fusion or lumbar laminectomy and posterolateral fusion will be enrolled in the study and consented for intraoperative single-dose methadone administration or standard narcotic regimen administration in a 1:1 block randomization plan. Patient may undergo one or two spinal level fusions and in blocks of 5, will be assigned to intervention or control groups in a manner that will be blinded to both the clinical team and the patients.

o Exclusion criteria:

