Age <21 or >80, renal failure requiring dialysis or serum creatinine greater than 2.0, significant hepatic dysfunction (liver function tests greater than twice the upper limit), hepatic cirrhosis, pulmonary disease requiring home oxygen therapy, obstructive sleep apnea, severe heart disease, allergy to methadone, morphine, ketamine or fentanyl, **recent or distant history of opioid abuse,** opioid use equal to or greater that the equivalent of 10mg morphine per day, poorly managed psychiatric illness, a known history of alcohol abuse, morbid **obesity (for the purposes of this study body mass index > 50 kg/m2),** treatment with other NMDA receptor antagonists, HIV-1 protease inhibitors, erythromycin or ketoconazole, prolonged QTc on pre-operative EKG, and the refusal or inability to sign the consent form to agree to participate in this study.

State primary and secondary outcome(s)

The primary outcomes for the study include total narcotic dose post-operative, frequency of narcotic use, the time to first ambulation after surgery with PT, length of stay, disposition (i.e. level of rehabilitative care), and improvement on clinical questionnaires in the intervention group as compared to the control group. Secondary outcomes include better subjective pain control, need for post-operative course of

dexamethasone for post-operative/post-fusion radiculopathy or neurapraxia/neuropathy and fusion at 3-6 months.

> For Randomized clinical trials

• Indicate whether a parallel or crossover study, and the number of treatment groups
The study will take the form of a parallel, 2 arm analysis of a methadone treatment group or a
group receiving the current standard of care without intra-operative methadone administration.

• Describe randomization and blinding procedures

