The outcome measures, will serve to compare to the standard narcotic regimen controls by demonstrating the effect of methadone on postoperative pain use, rehabilitation time, and validated clinical measures. Control patients will have undergone the same 1 or 2 level lumbar fusions for lumbar stenosis with administration of standard narcotic regimen intra-operatively and post-operative patient controlled analgesia usage. We anticipate that with 60 patients per group, the randomization will create similar groups of patients with which we can accurately compare our outcome measures. Other than intraoperative narcotic administration, all other portions of the intra-operative and post-operative care will remain the same for control and intervention patients.

3) Study Population

Describe the study population: number, age range; health status or other characteristics pertinent to the study

The study population will consist of 120 patients between the ages of 21 and 80 who will be undergoing lumbar fusion surgery. The patients will be either ASA grades I-III and will meet the inclusion criteria as listed above. They will be required to have no significant narcotic abuse or significant use (>10mg equivalents of morphine per day) in the past and should not be on medications that may induce or inhibit the metabolism of methadone. They must not meet any of the exclusion criteria stated above.

Describe how the sample size and power of the study were determined, including the statistical approach and any assumptions on which the calculations are based.

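### Time to first ambulation has no rule for patients who have not walked with PT by discharge, and late walkers can be t-tested, rank-tested or deleted at the analyst's choice

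*Combined protocol and SAP*

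**What the plan says.** **The outcome.** The title is "Single-dose Intraoperative Methadone for Early Ambulation and Sustained Pain Control in Spinal Fusion Surgery Patients". Section 2, under primary and secondary outcomes, lists "the time to first ambulation after surgery with PT" among six primary outcomes. Section 7(a) includes time to ambulation in the tested hypothesis.

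**Who may enter.** The inclusion text in section 2 reads "Patients undergoing elective lumbar transforaminal interbody fusion or lumbar laminectomy and posterolateral fusion will be enrolled in the study", limited to one or two levels. The exclusion list opens with "Age <21 or >80, renal failure requiring dialysis or serum creatinine greater than 2.0" and runs through hepatic, pulmonary, cardiac, allergy, opioid, psychiatric, alcohol, weight, drug-interaction, QTc and consent items. None concerns walking or motor deficit. Section 3 adds "The patients will be either ASA grades I-III and will meet the inclusion criteria as listed above", which is not a walking criterion either.

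**Baseline status.** The confounding paragraph of section 7 first credits the strict eligibility criteria, then says "Patient time to ambulation will be confounded by baseline neurological status" and offers random assignment as the remedy. No stratum, covariate or baseline walking measure is planned.

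**Analysis.** Section 7(a) plans two-sample t-tests, including for time to ambulation. It moves to a Wilcoxon rank-sum test if values lie more than 5 MAD (median absolute deviations) from the median and there is worry that individual patients distort the result. It also lets outliers be excluded if they would materially change the mean. The sample-size paragraph of section 3 allows exclusion of unusual post-operative courses judged unrelated to pain control. In justifying t-tests for pain scores, it states generally that "there will be no censoring of the study data".

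**The concern.** Randomisation balances patients with poor baseline walking on average. It does not give them a usable outcome. A patient who could barely walk or not walk before surgery will probably have either no time to first ambulation with PT or a very late one, and the plan fixes the handling of neither.

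With no value, the patient leaves the comparison because of how the outcome turned out. With a late value, the same patient can be handled in three ways, chosen after the data are seen. For an outcome named in the title, the set of patients analysed and the test used should not depend on the values observed. If late values are kept and the t-test is used, they inflate the variance and dilute the effect, so a real benefit may be missed.

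**Working it through.** **Inputs from the documents.** 60 per arm, 1:1; significance level 0.05 (sidedness not stated); effect 0.56 within-group SD; 51 per group calculated for 80% power; SD of 6.7 days, for time to discharge only.

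**Assumed inputs.** The documents give no SD for time to ambulation and no share of non-walkers. I take walkers with mean 1.5 days and SD 1.0 day (gamma-shaped), an effect of 0.56 SD in walkers, and a fraction p of 2%, 5% or 10% (2.4, 6 or 12 of 120) who have no value or enter at day 5 or day 10.

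**1. The plan's own figure.** n per arm = 2(1.96 + 0.8416)² / 0.56² = 15.70 / 0.3136 = 50.06, rounded up to 51. This matches, two-sided (one-sided would give 40). At 60 per arm, power = Φ(0.56 × √30 − 1.96) = Φ(1.107) = 0.866, or 0.860 by the t distribution. Also 0.56 × 6.7 = 3.75 days, the plan's 3.8.

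**2. Patients with no value.** They simply leave the t-test:

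| Analysed per arm | Power at 0.56 SD |
|---|---|
| 60 | 0.860 |
| 57 | 0.842 |
| 54 | 0.822 |
| 51 | 0.800 |

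The power cost is small. The problem is that the exclusion depends on the outcome.

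**3. Late values kept in a t-test.** With late value L, the variance is about 1 + p(1 − p)(L − 1.5)² and the mean effect shrinks to 0.56(1 − p). For p = 5% and L = 10: variance = 1 + 0.0475 × 72.25 = 4.43, SD = 2.105, standardised effect = 0.532 / 2.105 = 0.253, power = Φ(0.253 × √30 − 1.96) = 0.28. Simulation gives about 33% for the same case.

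**4. Power by analysis route (simulation, 60 per arm).**

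| Route | p = 2% | p = 5% | p = 10% |
|---|---|---|---|
| t-test, day 5 | 78% | 67% | 53% |
| t-test, day 10 | 54% | 33% | 18% |
| Switch to Wilcoxon whenever the 5-MAD flag fires, day 5, raw MAD | 91% | 85% | 68% |
| Same, day 5, MAD scaled by 1.4826 | 82% | 71% | 56% |
| Same, day 10 | 92% | 87–88% | 78–79% |
| Wilcoxon fixed in advance, non-walkers ranked worst | 92% | 88% | 80% |

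With no non-walkers, the t-test has 86% and the Wilcoxon test 93% under this skewed shape.

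**5. Check with a normal outcome.** Baseline power is 0.86 (t-test) and 0.84 (Wilcoxon). One extreme patient per arm at 5, 7 or 10 SD cuts the t-test to 0.75, 0.62 or 0.40. Three per arm cut it to 0.46, 0.21 or 0.02. The Wilcoxon test holds 0.82–0.83 and 0.78. At 3 SD the 5-MAD flag rarely fires (11–26% of runs with raw MAD, 0% with scaled MAD), yet three such patients per arm take the t-test to 0.70.

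**6. Type I error.** With no treatment effect and extreme patients split at random, the t-test rejects in 0.02 to 0.055 of runs.

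**The case against.** The strongest reply is that the t-test is not the whole plan. Section 7(a) names a rank test for outlying values, and step 4 shows that it recovers nearly all the power at day 10 and most of it at day 5 under the literal (raw) MAD. A reader might infer that a few non-walkers will swamp the planned analysis. The documents do not support that, because it treats the fallback as never used. What remains is that the fallback also needs a judgement that individual patients distort the result, the MAD scaling is undefined, moderately late values are not flagged, and the same paragraph permits deletion instead.

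Second, missing values cost little, and walking status precedes randomisation, so losses should be similar between arms. This stands for patients who could not walk whatever the treatment. It does not cover a slow walker discharged before walking, because the hypothesis is that methadone changes that time.

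Third, section 2 makes ambulation one of the discharge milestones, so perhaps everyone obtains a value. If so, the result is a late value instead of a missing one, and the choice between t-test, rank test and deletion remains open.

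Fourth, such patients may be rare in elective one- or two-level fusion. That is plausible, but the documents give no frequency either way.

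Fifth, relying on randomisation against confounding is valid. I agree; the gap concerns how the outcome is scored, not imbalance between arms.

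**Conclusion.** The point holds as a gap in the analysis specification for a title and primary outcome. A patient who has not walked with PT by discharge is unscored, and a very late walker can be handled in three ways chosen after the data are seen. The harm is outcome-dependent exclusion and analyst discretion, plus lost power if late values stay in a t-test: from about 86% to between 78% and 18% across the assumed range. If the rank-test switch is applied whenever its flag fires, power is 78–92% at day 10 and 56–91% at day 5, depending on the share of non-walkers and the MAD scaling.

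Two further inferences are not supported. Late values do not inflate type I error (0.02 to 0.055 under no effect). Nor do the documents show that patients unable to walk must be excluded: a worst-rank rule keeps 92%, 88% and 80% power with them enrolled, and an exclusion would narrow the population for the other five primary outcomes. All the power losses rest on an assumed share of non-walkers, SD and late day. The missing scoring rule rests on no assumption.

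**What to change.** In section 7(a), make these changes for time to first ambulation:

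- Make the Wilcoxon rank-sum test the pre-specified analysis, not a fallback.
- Keep every randomised patient, and give the worst (tied) rank to anyone who has not walked with PT by discharge.
- State that neither the outlier deletion in section 7(a) nor the unusual-course exclusion in section 3 applies to this outcome.
- Correct the no-censoring statement in section 3 to agree, and say how the rule fits with section 7's removal of certain in-hospital deaths from the analysis.

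Also record pre-operative walking ability at screening, so that the comparison can be adjusted or stratified for it.

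The cost is a few sentences and one screening field, with no extra patients or procedures. The small downside is that the result is a rank comparison and not a difference in mean days; the mean difference can still be reported descriptively. Excluding patients unable to walk before surgery is optional and is the sponsor's choice.
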